3 OBJECTIVES AND ENDPOINTS

Table 2 - Objectives and endpoints

Objectives	Endpoints
Primary 
Phase 1: To characterize the safety and tolerability of isatuximab in kidney transplant candidates.Phase 2: To evaluate the efficacy of isatuximab in desensitization of patients awaiting kidney transplantation.	
Adverse events (AEs)/serious adverse events (SAEs) and laboratory abnormalities.Response rate (RR) defined as the proportion of participants meeting at least one of the predefined desensitization efficacy criteria, from baseline up to 26 weeks after treatment period, measured by single antigen bead (SAB) assay per central laboratory assessment as follows:
Reduction in calculated panel reactive antibodies (cPRA) resulting in at least 100% increase of likelihood of finding a compatible donor (for target cPRA, see Section 10.9).Reduction in antibody titer ($\geq 75\%$ reduction from baseline) to achieve target cPRA (see Section 10.9).Elimination of ≥ 1 anti-HLA-antibody (ie, mean fluorescence intensity [MFI] reduced to <2000) as measured by a SAB assay, for antibodies with baseline MFI ≥ 3000.
Secondary 
Phase 2: To characterize the safety profile of isatuximab in kidney transplant candidates.To characterize the pharmacokinetic (PK) profile of isatuximab in kidney transplant candidates.To evaluate the immunogenicity of isatuximab.To assess the overall efficacy of isatuximab in desensitization of patients awaiting kidney transplantation.	
AEs/SAEs, and laboratory abnormalities.PK parameters of isatuximab (see Table 7)Incidence of anti-drug antibodies (ADA) against isatuximab.Duration of response (DoR) per central laboratory assessment.Proportions of participants and duration achieving target cPRA per local laboratory assessment.Number of anti-HLA-antibody with baseline MFI ≥ 3000 reduced to <2000 as measured in a SAB assay per central laboratory assessment.Transplantability including time to first transplant offer, time to transplant, and number of transplant offers, if applicable.Time to first AMR episode and rate of AMR, if applicable.Graft survival at 6 months post-transplant, if applicable.

Objectives	Endpoints
Tertiary/exploratory	

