9.4.1 Efficacy analyses

Analysis of primary efficacy endpoint:

- In Phase 2, the RR by cohort will be summarized using descriptive statistics. A 95% 2-sided confidence interval will be computed using the Clopper-Pearson method ([Table 9](#)).

Analyses of secondary endpoints:

- All secondary endpoints (if applicable) during Phase 2 will be summarized descriptively and presented by cohort. Categorical variables (eg, rates and proportions) will be tabulated

via frequency distributions. Continuous variables (eg, change from baseline) will be summarized by providing the number of observations (n), mean, median, standard deviation, minimum, and maximum. Duration of response and other time to event variables will be analyzed using the Kaplan-Meier method ([Table 9](#)). Participants not reaching an event will be censored at their last follow-up visit.

- No hypothesis/significance testing will be performed.

Table 9 - Efficacy analyses

Endpoint	Statistical Analysis Methods
Primary: Response rate (per central laboratory)	Descriptive statistics and Clopper-Pearson method
Secondary:	

 • Rate/Proportion of participants: 
 - achieving target cPRA (per local laboratory) - with AMR (if applicable) - with graft survival at 6 months post-transplant (if applicable) 	Descriptive statistics

 • Number of: 
 - anti-HLA-antibody eliminated (per central laboratory) - transplant offers (if applicable) 	Descriptive statistics

 • Duration of: 
 - response (DoR) (based on central laboratory) - achieving target cPRA (based on local laboratory) 	Kaplan-Meier method

 • Time to event: 
 - first transplant offer - transplant (if applicable) - first AMR episode (if applicable) 	Kaplan-Meier method
Tertiary/Exploratory	Will be described in the SAP and finalized before the database lock.

Abbreviations: AMR = antibody mediated rejection, cPRA = calculated panel reactive antibodies, DoR = duration of response, HLA = human leukocyte antigen, SAP = statistical analysis plan.

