The study will have a screening period of up to 28 days, a treatment period of up to 12 weeks, a site visit follow-up period (FUP) of up to 26 weeks, and an extended FUP which include telephone contacts every 90 days and information collection until study cut-off, death, or lost to follow-up. The study cut-off is planned at 26 weeks after the last participant completes the treatment period, or when the last ongoing participant is lost to follow-up, whichever is earlier. The Sponsor (Sanofi) may choose to extend the study cut-off date depending on the enrollment rate observed to facilitate adequate follow-up data collection. Participants who wish to proceed to transplantation when a compatible donor becomes available while on study must discontinue IMP immediately, complete an early discontinuation (E/D) visit prior to transplantation if clinically feasible, and proceed to extended FUP. The study duration that involves site visit per participant (ie, screening, treatment, site visit FUP) will be approximately 42 weeks. The study duration including extended FUP per participant will be approximately 78 weeks (depending when the participant is enrolled).

Treatment period: The cycle duration is 28 days and a complete treatment period is comprised of 3 cycles of IMP treatment. Participants will continue treatment until receiving 3 cycles of IMP, unacceptable AE per Investigator's judgment, or participants' decision to stop the treatment.

Site visit FUP: Participants completing the treatment period and who are able to remain on study will return to the study sites for study procedures.

Extended FUP: The following participants will be followed-up every 90 days by phone calls, until study cut-off date, death, or lost to follow-up, whichever comes first:

- Participants who completed or discontinued from site visit FUP
- Participants who proceed to transplantation during treatment period or site visit FUP.

During extended FUP, specified information per protocol will also be collected by study site (see protocol section 1.3).

Below figures show the study schema and duration of study period:

Figure 1 - Graphical study design

[figure not shown]
[figure not shown]

Figure 2 - Duration of study period (per participant)

Details on schedule of activities (SoA) are provided in protocol section 1.3.

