Graft survival rate at 6 months post-transplant: defined as proportion of participants with graft survival status at \leq 6 months post-transplant="Functioning". Study eCRF FOLDER/page for date of biopsy with AMR: TRANSPLANT/GRAFT SURVIVAL AT LESS THAN OR EQUAL TO 6 MONTHS

In addition, the proportion of participants with a functioning graft beyond 6 months post-transplant may be tabulated, if data are available. An adhoc analysis of graft survival may also be performed using the Kaplan-Meier method.

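### The 6-month graft survival rate counts grafts whose follow-up ends before 6 months while still functioning, so among transplanted participants it can be overstated

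*SAP*

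**What the plan says.** The protocol lists the endpoint as "Graft survival at 6 months post-transplant, if applicable" (Section 3, Table 2), and Table 9 in Section 9.4.1 plans descriptive statistics for it. SAP 4.4.2.1 turns it into a calculation: "Graft survival rate at 6 months post-transplant: defined as proportion of participants with graft survival status at" no more than 6 months after transplant equal to functioning. The source is the eCRF page "TRANSPLANT/GRAFT SURVIVAL AT LESS THAN OR EQUAL TO 6 MONTHS". A tabulation beyond 6 months is optional, and so is the time-to-event version: "An adhoc analysis of graft survival may also be performed using the Kaplan-Meier method".

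Three other places bear on it.

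- SAP 5.4.1 bases percentages on participants with a non-missing observation in the population considered. For graft survival that population is not named. For time to first AMR, by contrast, SAP 4.4.2.1 excludes participants who were not transplanted.
- SAP 1.1 fixes the end of data collection by treatment, not by transplant: "The study cut-off is planned at 26 weeks after the last participant completes the treatment period", or earlier if the last ongoing participant is lost to follow-up. The sponsor "may choose to extend the study cut-off date depending on the enrollment rate observed".
- SAP 5.2 declares no changes to the protocol-planned analyses.

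**The concern.** Survival at 6 months and a functioning status at some time up to 6 months are different quantities. They agree only if every graft is followed for 6 months and the status used is the one at the end of that period. The SAP secures neither. A graft seen working at week 3, in a participant whose follow-up then ends at cut-off, has a non-missing status. Under the SAP's percentage rule it enters both numerator and denominator as a success, and the unobserved months are counted as survival.

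This is the only listed secondary endpoint that asks whether kidneys transplanted after desensitization keep working. A reader will take a figure labelled 6-month graft survival at face value.

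**Working it through.** **Timeline inputs (SAP 1.1).** The plan has "a screening period of up to 28 days, a treatment period of up to 12 weeks", then up to 26 weeks of site-visit follow-up. The plan's own figure reproduces: 28/7 + 12 + 26 = 42 weeks, as stated. The stated total of about 78 weeks, less 4 weeks of screening, leaves 74 weeks from first dose. The last-treated participant has 12 + 26 = 38 weeks from first dose to the planned cut-off.

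**Who falls short.** Take 6 months as 26 weeks.

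- Typical participant: 74 − 26 = 48, so transplants after week 48 have under 6 months of graft follow-up. Treatment plus site-visit follow-up ends at week 38, so transplants within that span are fully followed.
- Last-treated participant: 38 − 26 = 12, so any transplant after the end of treatment falls short.

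**Size.** The documents give no transplant times and no graft-loss rate, so these are assumptions: transplant times uniform from first dose to cut-off, constant loss hazard, and the latest status up to 6 months used. Let q be the true 6-month loss and F the weeks from first dose to cut-off.

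- Share of grafts cut short: s = 26/F, which is 26/74 = 0.351 or 26/38 = 0.684.
- Mean observed loss in those grafts: f = 1 − q/(−ln(1 − q)). For q = 0.10, f = 1 − 0.10/0.10536 = 0.0509. For q = 0.20, f = 1 − 0.20/0.22314 = 0.1037.
- Reported loss = (1 − s)q + s·f.

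| True loss | F = 74 (typical) | F = 38 (last-treated) |
|---|---|---|
| 10% | 0.649 × 0.10 + 0.351 × 0.0509 = 8.3% | 0.316 × 0.10 + 0.684 × 0.0509 = 6.6% |
| 20% | 0.649 × 0.20 + 0.351 × 0.1037 = 16.6% | 0.316 × 0.20 + 0.684 × 0.1037 = 13.4% |

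**Why the choice of status matters.** Take an invented case of 10 transplants. Six are followed for the full 6 months, and one of these functions at month 3 and fails at month 5. Four are cut off at months 1 to 4, all functioning. If any functioning status suffices, the rate is 10/10 = 100%. With the latest status it is 9/10 = 90%. Kaplan-Meier has 6 grafts at risk at month 5 and gives 5/6 = 83.3%. The SAP wording does not choose between the first two.

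**A tempting repair that fails.** Suppose the proportion keeps only grafts with a status at or after 6 months, or with failure before then. Early failures among short-follow-up grafts stay in, while the functioning ones drop out. Reported loss becomes [(1 − s)q + s·f] / [(1 − s) + s·f]. For a true 10% this is 0.0827/0.6665 = 12.4% (F = 74) or 0.0664/0.3506 = 18.9% (F = 38). Those errors, +2.4 and +8.9 points, exceed the −1.7 and −3.4 points of the SAP rule.

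**The case against.** The case for leaving the text alone has several parts.

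- A reader might infer that one functioning status at any check is enough. The SAP does not say so. It cites a single page for the period up to 6 months, and on that page an early failure may well be recorded as not functioning. The eCRF is not among the documents. This stands, which is why the figures above use the latest-status reading. The SAP's silence on the choice remains a gap.
- A reader might infer that most transplants made possible by a response fall short. That is true only for participants treated near the end. For a typical participant, transplants up to week 48 are fully followed. This stands.
- The sponsor may extend cut-off to improve follow-up. It may, but this is an option linked to enrolment rate, with no commitment to 6 months after the last transplant.
- Kaplan-Meier is already mentioned. It is optional, so the planned figure remains the proportion.
- The effect is small next to the noise. At the typical duration it is 1.7 points on a 10% loss. The study expects 24 to 42 participants, only some of whom will be transplanted, and with 10 transplants one graft is 10 points. The endpoint is untested and conditional on transplants occurring. All this stands, and it limits the point to an improvement that should be made. It does not justify a label that differs from what is measured.

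**Conclusion.** The definition in SAP 4.4.2.1 does not estimate graft survival at 6 months when follow-up is incomplete. Among transplanted participants it can overstate survival, and does so in expectation. Under the stated assumptions the overstatement is about 1.7 points (typical duration) to 3.4 points (worst case) for a true 10% loss, and 3.4 to 6.6 points for a true 20% loss.

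It would go too far to say that the rate is overstated. In a given dataset the error appears only if a graft fails after the status that was counted. The unnamed denominator could also push the other way: if untransplanted participants were included, the rate would be too low. The actual size is unknown because transplant timing and graft loss are not given. The primary response rate is unaffected.

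**What to change.** In SAP 4.4.2.1:

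- Name the population as transplanted participants, as is already done for time to first AMR.
- Make the Kaplan-Meier estimate at 6 months from the transplant date the planned analysis. The event is graft failure, with censoring at the last known graft status. State how death with a functioning graft is handled.
- Report the number at risk at 6 months and the number with under 6 months of follow-up.
- Confirm that a graft-failure date is captured. Footnote o of the protocol's schedule of activities (Section 1.3) lists graft survival status without a date, and extended follow-up calls are every 90 days. If a failure is known only to lie between two contacts, state the dating convention.
- If a simple proportion is also shown, restrict it to participants transplanted at least 6 months before cut-off, whatever their outcome. Do not select on having either a late status or an early failure, for the reason worked out above.
- Correct the eCRF pointer for this endpoint, which is labelled as an AMR biopsy date although it leads to the graft survival page. This looks like a copying slip.

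The cost is mainly SAP wording, plus a data-collection check on failure dates. The reported figure is likely to be slightly less favourable and its interval wider.

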4.4.2.2 Main analytical approach

All secondary efficacy endpoints (if applicable) during Phase 2 will be summarized descriptively and presented by cohort. Categorical variables (eg, rates and proportions) will be tabulated via frequency distributions (ie, number and percents). Continuous variables (eg, change from baseline) will be summarized by providing the number of observations (n), mean, median, SD, minimum, and maximum.

DoR and other time to event variables will be analyzed using the Kaplan-Meier method (ie, median and associated 95% confidence interval). No hypothesis/significance testing will be performed.

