- do not complete site visit follow-up period (FUP), after agreement with Medical Monitor.

Intervention groups and duration:

All participants will receive isatuximab monotherapy and the planned treatment duration is 3 cycles (each cycle is 28 days).

Starting dose and de-escalation design:

Starting dose is 10 mg/kg once weekly (QW) for 4 weeks followed by once every 2 weeks (Q2W). If the SD is determined not to be sufficiently well-tolerated, 6 additional (minimum) safety evaluable participants will be enrolled at DL-1. Dose levels and schedule for Phase 1 are detailed in [Table 1](#).

Overall safety monitoring will also be performed throughout the conduct of the study.

Table 1 - Dose level and schedule in Phase 1

Dose Level	Isatuximab
	1 cycle = 4 weeks (28 days)
SD	10 mg/kg QW × 4 for Cycle 1 → Q2W for cycles 2 and 3
DL-1	5 mg/kg QW × 4 for Cycle 1 → Q2W for Cycles 2 and 3

Abbreviations: DL-1 = dose level minus 1, QW = once weekly, Q2W = once every 2 weeks, SD = starting dose

Duration of study period (per participant):

The study will have a screening period of up to 28 days, a treatment period of up to 12 weeks, a site visit FUP of up to 26 weeks, and an extended FUP which include telephone contacts every 90 days and information collection until study cut-off, death, or lost to follow-up. The study cut-off is planned at 26 weeks after the last participant completes the treatment period, or when the last ongoing participant is lost to follow-up, whichever is earlier. The Sponsor may choose to extend the study cut-off date depending on the enrollment rate observed to facilitate adequate follow-up data collection. Participants who wish to proceed to transplantation when a compatible donor becomes available while on study must discontinue IMP immediately, and complete an early discontinuation (E/D) visit prior to transplantation if clinically feasible, and proceed to extended FUP. The study duration that involves site visit per participant (ie, screening, treatment, site visit FUP) will be approximately 42 weeks. The study duration including extended FUP per participant will be approximately 78 weeks (depending when the participant is enrolled).

Treatment period: The cycle duration is 28 days and a complete treatment period is comprised of 3 cycles of IMP treatment. Participants will continue treatment until receiving 3 cycles of IMP, unacceptable AE per Investigator's judgment, or participants' decision to stop the treatment.

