Figure 3 - Relationship between cPRA and likelihood of finding a compatible donor

Abbreviations: cPRA = calculated panel reactive antibodies, cPRAd = calculated panel reactive antibody with decimals, LCD = likelihood of compatible donor

The median waiting time to transplantation in the US was reported to be 4 years, while sensitized patients often endure waiting times exceeding 5 years (3, 23). With the introduction of the Kidney Allocation System (KAS) in December 2014 giving highly sensitized patients additional points, the deceased donor transplantation rate became more balanced across different cPRA compared to pre-KAS (increased transplantation rate in patients with cPRA 90% to 99.9%) (24). However, access to transplant remains considerably lower post-KAS for candidates with cPRA >99.9% who are considered as “difficult-to match” patients (25). In addition, the transplant rate for cPRA 80% to 89% candidates decreased, and the waitlist mortality continued to increase for very highly sensitized patients with cPRA ≥98% compared to other patients (24). The long-term risk of death is significantly lower in patients who undergo transplantation compared to patients who remain on the waitlist and continue dialysis (relative risk 0.32; P <0.001) (26). In addition, prolonged

dialysis has resulted in shorter patient and graft survival after transplantation (27, 28). An unintended consequence of KAS is the disproportionate allocation of highest quality of kidneys (kidney donor profile index ≤ 20) in highly sensitized patients (cPRA $\geq 99\%$) which is correlated with survival, which created a disadvantage for the majority of other kidney transplant waitlist candidates (cPRA $< 99\%$) (29). National prioritization access programs similar to KAS have been implemented by ex-US countries (eg, ETKAS by Eurotransplant, PATHI in Spain). While it may be unattainable to achieve a system with absolutely no undesirable disparities in access to transplantation, a standardized desensitization therapy that can effectively convert HLA sensitized patients to lower cPRA levels (eg, non-sensitized or less sensitized) would help to further resolve the imbalance in kidneys allocation, and/or reduce the need to transport donor organs across long distance for those who requiring expanded access to match with a compatible donor organ.

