4 STATISTICAL ANALYSES

4.1 GENERAL CONSIDERATIONS

In general, continuous data will be summarized using the number of observations available, mean, standard deviation (SD), median, minimum, and maximum. Categorical and ordinal data will be summarized using the count and percentage of participants. Time to event variables will be analyzed using the Kaplan-Meier method.

The baseline value is defined as the last available value before the first dose of IMP. For participants enrolled but not treated, the baseline value is defined as the last available value before enrollment.

Analyses will be performed by cohort (and overall) within Phase 2, for demographics and baseline characteristics. If Phase 1 dose level is reduced due to unacceptable toxicities, summaries may also be performed on Phase 1 participants, by dose level group.

Observation period

The observation period will be divided into 3 segments:

- The **pre-treatment period** is defined as the time from when the participants give informed consent to first IMP administration.
- The **on-treatment period** (ie, treatment-emergent [TE] period) is defined as the period from the first IMP administration to the last IMP administration + 30 days.
- The **post-treatment period** is defined as the time starting 31 days after the last dose of IMP to study cut-off.

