Number of anti-HLA-antibody with baseline MFI \geq 3000 reduced to $<$ 2000 as measured in a SAB assay per central laboratory assessment

Reduction of anti-HLA-antibody is defined similarly as in RR criterion 3 ([Section 4.3.1](#)), and will be summarized by the proportion of participants with pre-specified ranges of anti-HLA-antibody reduction (eg, none, 1-5, >5-10, >10-15, ... >x).

Transplantability including time to first transplant offer, time to transplant, and number of transplant offers, if applicable

Time to first transplant offer: defined as time from date of first IMP dose up to date of first transplant offer. Study eCRF folder/page for transplant offer: TRANSPLANT/TRANSPLANT STATUS

Time to transplant: defined as time from date of first IMP dose up to date of kidney transplant on/after first IMP start date. Study eCRF FOLDER/page for date of kidney transplant surgery during study: TRANSPLANT/TRANSPLANT STATUS; KIDNEY TRANSPLANT SURGERIES [Transplant and Patient status subcategory=During study, and corresponding Date of kidney transplant]

Participants who do not receive any transplant offer or any transplant, and:

- who died will be censored at the longest follow-up date across all participants in the study prior to the analysis cut-off date.
- who are still alive will be censored at the participant's last laboratory assessment date collected in the study or at the analysis cut-off date, whichever is earlier.

Time to first AMR episode and rate of AMR (if applicable)

Time to first AMR: defined as time from date of first IMP dose up to date of biopsy with first AMR. Study eCRF FOLDER/page for date of biopsy with AMR: TRANSPLANT/GRAFT REJECTION BIOPSY

Transplanted participants without any AMR will be censored at the participant's last assessment/contact date collected in the study or at the analysis cut-off date, whichever is earlier. Participants who do not receive a transplant in the study will be excluded from this analysis.

Rate of AMR: defined as proportion of participants with AMR field ticked as "yes" based on graft rejection biopsy eCRF page. Study eCRF FOLDER/page for AMR: TRANSPLANT/GRAFT REJECTION BIOPSY

Graft survival rate at 6 months post-transplant (if applicable)

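### For time to transplant the SAP names only a Kaplan-Meier median, which the planned follow-up will seldom validly reach; fixed-time probabilities and a corrected censoring date are needed

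*SAP*

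**What the plan says.** SAP 4.1 says only that "Time to event variables will be analyzed using the Kaplan-Meier method". SAP 4.4.2.2 narrows this to a specific output: "DoR and other time to event variables will be analyzed using the Kaplan-Meier method (ie, median and associated 95% confidence interval". Protocol 9.4.1 and its Table 9 name the Kaplan-Meier method for time to first offer, time to transplant and time to first AMR, without listing the estimates to be reported.

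The transplant endpoint is "Time to transplant: defined as time from date of first IMP dose up to date of kidney transplant on/after first IMP start date" (SAP 4.4.2.1). Under that section, living participants without an offer or transplant are censored at their last laboratory assessment or the analysis cut-off, whichever is earlier. Protocol 9.4.1 instead censors at the last follow-up visit, and SAP Appendix 2 declares no change from the protocol.

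On background waits, Protocol 2.1.1 says "The median waiting time to transplantation in the US was reported to be 4 years" and that "sensitized patients often endure waiting times exceeding 5 years". On follow-up, the synopsis says "The study duration including extended FUP per participant will be approximately 78 weeks", and SAP 1.1 gives "a treatment period of up to 12 weeks, a site visit follow-up period (FUP) of up to 26 weeks". Each cohort has at least 12 participants, with up to 6 replacements.

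**The concern.** A Kaplan-Meier median exists only once the estimated event-free proportion falls to one half. If background waits are several times longer than follow-up, few cohorts of 12 to 18 will get there, and the one estimate the SAP names will usually be missing. When it does appear, it comes from the sparse end of the curve.

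Transplantability is the secondary endpoint that connects antibody reduction to patient benefit. A reader of the report would want the chance of transplant by a stated time. The same fit yields that figure, but the SAP does not ask for it.

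The censoring rule makes this worse. Transplants and offers are collected through extended follow-up, whereas scheduled central laboratory draws stop with the site visits. Censoring at the laboratory date while counting later events can produce a median that is far too short.

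**Working it through.** The plan gives no operating figure for these endpoints, so there is none to reproduce. Its sample-size statement concerns the response rate, and the rates in it are redacted.

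**Inputs**
- Background median wait: 4 years = 208 weeks, and 5 years = 260 weeks (Protocol 2.1.1). The second is stated as what sensitized patients often exceed, not as a median. It is used here as one.
- Doubled transplant rate: 260 / 2 = 130 weeks.
- Average follow-up from first dose: 78 − 4 weeks of screening = 74 weeks. The last participant has 12 + 26 = 38 weeks at the planned cut-off.
- Assumptions: exponential waiting times and no deaths. For staggered entry, follow-up is uniform from 38 to 110 weeks, which has mean 74. The upper limit of 110 is assumed.

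**Common 74 weeks of follow-up.** The event probability is p = 1 − 2^(−74/median). With n=12 the median is reached if at least 6 participants have the event, which is a binomial tail.

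| Median wait | p | Expected events of 12 | P(median reached), n=12 |
|---|---|---|---|
| 260 weeks | 17.9% | 2.1 | 1.1% |
| 208 weeks | 21.9% | 2.6 | 3.0% |
| 130 weeks (doubled rate) | 32.6% | 3.9 | 16% |

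**Staggered follow-up, 38 to 110 weeks (simulation).** Everyone is followed to cut-off.

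| Median wait | n=12 | n=18 |
|---|---|---|
| 260 weeks | about 9–10% | about 6% |
| 208 weeks | about 13% | about 10% |
| 130 weeks | about 32% | about 28% |

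At 4- to 5-year waits, a median that is printed rests on only about 2 to 3 participants still at risk.

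**Effect of the SAP's censoring date.** Follow-up Week 1 falls 15 days after Cycle 3 Day 15, so 70 + 15 = 85 days after first dose, or about week 12. Central draws then run every 4 weeks to follow-up Week 25, 24 weeks later, at about week 36. If no later laboratory date counts, every living event-free participant is censored at week 36. Those still at risk after that are then only participants with a recorded later event, so the curve runs to zero and one such event is enough to produce a median. With 74 weeks of follow-up and n=12:
- 260 weeks: 2^(−36/260) − 2^(−74/260) = 0.908 − 0.821 = 0.0875; 1 − (1 − 0.0875)^12 = 67%.
- 208 weeks: 0.887 − 0.781 = 0.1055; 1 − (1 − 0.1055)^12 = 74%.

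The staggered simulation agrees. A median appears in 64% to 74% of cohorts of 12, typically near week 53, when the true value is 208 to 260 weeks. The 52-week cumulative estimate averages about 32% against a true 13% (5-year wait), and about 37% against 16% (4-year wait). The 26-week estimate is unaffected.

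**What a fixed-time estimate would look like.** At 38 weeks the probability is 9.6% at a 260-week median and 18.3% at 130 weeks, so about 1 and 2 events of 12. Clopper-Pearson intervals are 0.2% to 38% for 1/12 and 2.1% to 48.4% for 2/12.

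**The case against.** Five points can fairly be made in the plan's defence.

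- **A reader might infer that these endpoints will yield no number at all.** The documents do not support that. With 12 participants, a log-log lower limit for the median exists from 2 events, which occurs in about 66% to 80% of cohorts at 4- to 5-year waits. The number of offers is reported separately. Under the laboratory-date rule, the likelier fault is a wrong number.
- **A reader might extend the result to time to first offer.** The quoted waits are to transplant. Offers can be declined, so first offers come no later than transplants and may be more common. If an assumed 20% of participants had an offer, the median would be reached in 2% of cohorts of 12. At 50% or 60% the figures would be 61% and 84%. The point is conditional there.
- **A reader might expect a fixed-time probability to reveal a doubled rate.** It would not: the two 38-week intervals above overlap almost entirely. The study is single-arm and these endpoints are descriptive.
- **The background waits may not fit this population.** Up to 6 living-donor participants in Cohort A would raise event rates, and cPRA of 99.90% or more would be expected to lower them. Neither is modelled.
- **Other summaries exist.** AMR is already reported as a proportion. Match-run simulations and matched controls also address transplantability. The SAP's exploratory-endpoint section is unreadable here, so further summaries in it cannot be excluded.

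All five stand as limits on the point. None supplies a fixed-time estimate of transplant in the readable plan, and none resolves the censoring date.

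**Conclusion.** The point holds for time to transplant. At the protocol's background waits, the only estimate SAP 4.4.2.2 names would be validly reached in about 6% to 13% of cohorts of 12 to 18 under staggered follow-up, and in 1% to 3% at n=12 with a common 74 weeks. A doubled transplant rate brings this to about 30% and 16% respectively.

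These figures rest on exponential waits, no deaths and the assumed spread of follow-up. The artefact further depends on whether laboratory dates from extended follow-up count as the last assessment, which the SAP does not say. If they extend to last contact, the artefact disappears and the median is again seldom reached.

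This is a reporting weakness in a descriptive secondary endpoint and does not touch the primary analysis.

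**What to change.** In SAP 4.4.2.2, for time to transplant and time to first offer, add the Kaplan-Meier cumulative probability with 95% CI at 26, 38 and 52 weeks from first dose, by cohort and with numbers at risk. Report the median only if it is reached.

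At the same time, in SAP 4.4.2.1, censor living event-free participants at their last transplant-status contact or the cut-off, instead of at the last laboratory date. The two changes belong together. Without the second, estimates after about week 36 are biased upward, the 52-week one above all, and only the 26-week estimate is safe.

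For AMR, rely on the count and proportion among transplanted participants that are already planned. At 4- to 5-year waits only about 2 to 4 per cohort would be transplanted (12 × 0.179 = 2.1; 18 × 0.219 = 3.9). Keep the median for duration of response.

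The cost is SAP wording and a few table rows from data already collected. The downside is visibly wide intervals. The gain is an interpretable estimate, not the power to detect a doubled rate.
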